7.2.14 Treatment Delivery

Patient Set Up and Verification Imaging:

Patients will be positioned for treatment on the treatment bed within their immobilization mask and aligned according to marks placed on this mask to indicate the isocenter. Image guided radiation therapy (IGRT) is to be completed to verify patient positioning. Daily IGRT is strongly recommended, however, the minimum requirement is weekly imaging, starting on the first day of treatment.

On-board volumetric imaging (e.g. kilovoltage (kV) or megavoltage (MV) conebeam CT (CBCT)) is recommended to be used and compared to the planning CT to verify daily positioning. Alternatively, this can be done with portal images of orthogonal fields localizing the isocentre placement for IMRT plans. Image matching will be based on alignment of regional boney landmarks with offsets of greater than 3 mm requiring patient repositioning. Imaging post-recommendation is recommended but not required.

7.2.15 Corrections For Radiotherapy Treatment Interruptions

Treatment interruptions of a single day will be compensated for with the addition of a second daily treatment on one day of the week preceding or following the interruption. These treatments should have a strict minimum interfraction interval of 6 hours. For patients receiving accelerated fractionation the compensatory second fraction should have a minimum two-day separation from the regularly scheduled two fraction day. A maximum of three such compensatory treatments will be permitted during the treatment course. Interruptions not compensated for will be recorded and accounted for in the determination of protocol compliance according to Section 7.2.16.

7.2.16 Compliance Criteria

Radiation treatment related deviations outside protocol recommendations and likely to influence clinical outcome will be considered as major. Such deviations could include failure to identify and treat appropriate targets and excessive treatment of non-target tissues. These determinations will be made during the plan review process. Deviations outside protocol recommendations and unlikely to influence clinical outcome will be considered as minor.

Treatment Interruptions:

Treatment breaks must be clearly indicated in the treatment record along with the reasons for the treatment breaks. Treatment breaks should be allowed only for resolution of severe acute toxicity and/or for intercurrent illness and not for social or logistical reasons

Single day interruptions will be compensated for according to guidelines in Section 7.2.15 for a maximum of 3 treatment day interruptions.

Any uncompensated treatment break(s) for any non-medical reason exceeding two sequential treatment days or 5 total days during the course of treatment will be considered as a protocol deviation.

Treatment interruptions of 3-5 sequential treatment days at a time for any reason will be considered a minor deviation and more than 5 sequential treatment days at a time will be considered as a major deviation.

Over the full course of treatment total treatment breaks of 6-10 days for any non-medical reason will be considered a minor deviation and if more than total 10 treatment days will be considered as a major deviation.

Dose Delivery

Major and minor dose delivery deviations for PTVs are described relative to dose objectives in the RTQA & Radiomics Manual on the HN.10 trial specific website. To be categorized as a major protocol deviation a plan will be determined to have i) failed to meet dose criteria and ii) such failure will have to be deemed as likely to have an adverse impact on patient outcome at the time of central review of the volumes and distributions.

The reviewers recognize achieving 100% of the dose to 95% of the Eval_PTVs will be challenging for cases in which the Eval_PTV is in close proximity to a critical OAR (Table 4) and/or skin surface, however these objectives would be expected to be achieved otherwise. Summary of minor and major deviations relating to target coverage is summarized in Table 7.

Non-compliance with the dose limitations assigned to critical OARs (Table 4) will always be considered a major deviation. Non-compliance with the dose limits of “other OARs” (Table 5) will be analyzed case per case by the reviewers to define if they should be considered deviations or not. Cases for which the doses to these OARs exceed the protocol limits due to proximity to PTVs will not be considered deviations. For example, exceeding dose limits to parotid glands is acceptable when needed to achieve acceptable dose to an adjacent or overlapping PTV.

Table 7: Major and Minor Dose Delivery Deviations for Planning target volumes.

	Eval_PTV_7000	Eval_PTV_5600	Eval_PTV_6300 (optional)	Dose Criteria for Deviations	
Percent Volume	(% of 70Gy)	(% of 56Gy)	(% of 63Gy)	Minor Deviation (% Volume)	Major Deviation (% Volume)
< 5%	< 100%	< 100%	< 100%		>5%
< 1%	< 93%	< 93%	< 93%	1-3%	>3%
0%	> 115%	> 125%*	> 120%*		
< 20%	> 110%	> 110%*	> 110%*		
Mean dose to Eval_PTV_7000	≤ 105%			105-107% of 70 Gy	>107% of 70 Gy

* These limits are applicable to portions of Eval_PTV_5600 and Eval_PTV_6300 which (i) do not overlap higher-dose PTVs and (ii) are not adjacent to higher-dose PTVs.

7.2.17 Central Radiotherapy Quality Assurance Review

Central quality assurance review of radiation delivery will consist of two components:

- i) real time rapid review of contoured targets (GTVs, CTVs, PTVs), OARs, and diagnostic imaging prior to commencement of treatment;
- ii) post treatment final review of radiotherapy plans.

Radiotherapy quality assurance reviews will be conducted centrally through QARC for all patients. Procedures, information and forms about the external review process can be found at <http://www.qarc.org>. Data required for plan documentation and quality assurance will be submitted according to QARC guidelines.

The real time rapid review and final review will be performed for every case.

Real Time Rapid Review:

The simulation scan, contours (targets and OARs as defined in Tables 2-5), diagnostic head and neck cross-sectional imaging (CT, MRI, PET), and supporting documentation is to be submitted and approved by QARC prior to commencement of treatment. This should be done as soon as possible to enable modifications to the contours to conform with the protocol. Feedback from the Rapid Review will be returned to the treating centre within 2 working days. The treating centre will implement corrective action if applicable and respond to QARC recommendations prior to commencement of treatment.

Final Review:

The required documentation is to be submitted to QARC within 2 weeks of treatment completion. A written report of the Final Review will be created by QARC. Additional details can be found in the RTQA & Radiomics Manual.

7.2.18 Central Review of Regional Failures

With reduction of the elective nodal irradiation volumes, there may be increased risk of out-of-field regional recurrence. Rigorous analysis of patterns of failure in the neck will be important for informing the results of this study and any future studies that utilize a similar treatment approach.

Any subject with regional recurrence in the lymph nodes of the neck (either as first or subsequent recurrence) will require central review of the radiological images (CT, MRI, and/or PET-CT) obtained at the time of recurrence in order to categorize the regional recurrence as in-field or out-of-field. The radiological images showing regional recurrence will be submitted within 4 weeks of confirming the recurrence.

The recurrent tumour volume will be identified on the earliest available diagnostic scan that shows the recurrent node. If the identified recurrent lymph node corresponds to a lymph node that was present on the planning scan, the node from the planning scan will be contoured and named “RECUR_NODE.” Otherwise, the identified recurrent lymph node volume will be contoured on the radiological images obtained at the time of recurrence and named “RECUR_NODE”; following registration to the planning scan, the RECUR_NODE volume will be transferred to the planning CT structure set.

The radiation dose received by the RECUR_NODE volume will be determined.

An “in-field regional recurrence” will be defined in cases in which $\geq 95\%$ of RECUR_NODE was within the 95% isodose of PTV_5600.

An “out-of-field regional recurrence” will be defined in cases in which $< 95\%$ of RECUR_NODE was within the 95% isodose of PTV_5600.

7.3 Surgical Treatment Plan of the Neck

Patients will have an evaluation of their primary tumour and neck (CT, MRI, and/or PET-CT) 12 weeks following the completion of radiotherapy (Section 5.0).

Institutional policies will be followed regarding surgical treatment of the neck for suspected residual, recurrent, or progressive nodal disease. Guidance is provided below regarding surgical treatment of the neck in specific settings. Regardless of the policy adopted for the management of the neck, any surgical intervention requires that new or persistent nodal disease be deemed operable by the treating surgeon.

7.3.1 Surgical Treatment Plan for Node-Positive Patients With Residual Abnormal Treated Lymph Nodes at 12 Weeks

The decision to undertake a neck dissection as a result of residual abnormal lymph nodes in the treatment field will be based on the clinical and radiographic examinations at 12 weeks post radiotherapy and institutional policies regarding planned neck dissections. Because of high rates of eventual CR in the neck for HPV positive patients presenting with involved lymph nodes coupled with low rates of pathologic positivity in residual nodes, it is suggested that centres follow the algorithm presented below:

Elective neck dissection should be completed ≤ 20 weeks following completion of radiotherapy.

Nodal disease* at week 12	Recommendation
No new or persistent disease	Follow as per protocol (Section 5.0)
Persistent treated nodes ≤ 2 cm	Repeat imaging in < 2 months
Persistent treated nodes > 2 cm with evidence of regression	Repeat imaging in < 2 months
Persistent treated nodes > 2 cm with no regression or progression compared to baseline	Neck dissection
Persistent treated nodes of any size with significant PET avidity (if performed as per institutional standards)	Consider neck dissection as per institutional policy
* on clinical and/or radiographic examinations	

7.3.2 Surgical Treatment Plan for Patients With New Abnormal Lymph Nodes

New lymph nodes that are abnormal based on the clinical and radiographic examinations at 12 weeks post radiotherapy or on any subsequent examinations should be biopsied without delay to confirm regional recurrence.

For a negative biopsy, at the discretion of the treating team, the subject may undergo re-attempt at biopsy, repeat imaging within 1-2 months, or proceed directly to prompt neck dissection.

For a positive biopsy, full re-staging examinations must be performed (Section 5.0). For isolated biopsy-proven regional recurrence, prompt neck dissection is recommended, provided that the disease is deemed to be operable by the treating surgeon. For inoperable isolated regional recurrence, salvage re-irradiation with or without concurrent chemotherapy may be employed at the discretion of the treating team. If there is overlap of the re-irradiation treatment field with the original treatment field, twice daily hyperfractionated radiotherapy should be performed in order to minimize potential late toxicity.

7.4 Concomitant Therapy

7.4.1 Permitted

Patients will receive ongoing supportive and symptom control (e.g. nutritional support including G tubes insertion, analgesics for pain) as indicated throughout the study. Other ancillary treatments such as intravenous hydration will be given as medically indicated. All treatment must be recorded in the case report forms.

7.4.2 Not Permitted

Administration of any other anti-cancer therapy is not permitted while the patient is receiving protocol therapy. Thereafter, patients may be treated at the investigator's discretion.

8.0 CRITERIA FOR MEASUREMENT OF STUDY ENDPOINTS

8.1 Definitions

8.1.1 *Evaluable for Adverse Events*

All patients will be evaluable for adverse event evaluation from the time of their first treatment.

8.1.2 *Evaluable for Quality of Life Assessment*

All patients who have completed the quality of life questionnaire are evaluable for quality of life.

8.1.3 *Evaluable for Health Economics Assessment*

All enrolled patients are evaluable for health economics. Those who have completed the resource utilization and lost productivity questionnaires will be evaluable for cost-utility analyses.

8.1.4 *Evaluable for Event-free Survival*

Event-free survival (EFS) is defined as the time from the date of registration to the date of first record of any of the following events:

- Investigator determined:
 - Local-regional progression or recurrence.
 - Distant metastasis.
- Surgery:
 - Surgery at any time for clinical or radiological (RECIST 1.1) disease persistence/progression/recurrence at the primary tumour site with tumour present/unknown on final pathology.
 - Neck dissection or surgery performed for clinical or radiological (RECIST 1.1) disease persistence/recurrence/progression within the target volumes > 20 weeks from the end of radiation therapy with tumour present/unknown on final pathology.
 - Neck dissection or surgery performed for clinical or radiological disease recurrence/progression outside the target volumes or without documentation of the site of failure at any time after registration with tumour present/unknown on final pathology.
- Non-protocol RT, chemotherapy, or biologic therapy (for the current cancer diagnosis) without documentation of the site of failure.
- Death due to any cause.

8.1.5 *Local-regional Control (LRC)*

Local-regional control is defined as the time from the date of registration to the date of any of the following, whichever comes first:

- Surgery of primary tumour at any time performed for clinical or radiological (RECIST 1.1) disease persistence/progression/recurrence with tumour present/unknown on final pathology

- Neck dissection > 20 weeks from the end of radiation therapy performed for clinical or radiological (RECIST 1.1) disease persistence/progression/recurrence within target volumes with tumour present/unknown on final pathology
- Neck dissection at any time after registration performed for clinical or radiological (RECIST 1.1) disease recurrence/progression outside the target volumes or without documentation of the site of failure with tumour present/unknown on final pathology.
- the first record of appearance (radiological or clinical) of local or regional disease progression/recurrence.

Distant recurrence/progression diagnosed before local-regional failure and death in absence of local-regional failure are not considered events of interest, but as competing risks events in the analysis of this endpoint. Subjects without any of the listed events (i.e. events of interest or competing risks events) are censored at the date of the most recent follow-up examination.

8.1.6 *Out-of-field Regional Control*

Time to out-of-field regional failure is defined as the time from the date of registration to the date of the first record of appearance of regional progression/recurrence outside the treatment field, or to the date of neck dissection at any time after registration with tumour present/unknown performed for clinical or radiological disease progression outside the target volumes, whichever comes first.

Local or distant recurrence/progression diagnosed before out-of-field regional failure and death in absence of out-of-field regional failure are not considered events of interest, but as competing risks events in the analysis of this endpoint. Subjects without any of the listed events (i.e. events of interest or competing risks events) are censored at the date of the most recent follow-up examination.

8.1.7 *Distant Metastasis Free Survival (DMFS)*

Distant metastasis free survival is defined as the time from the date of registration to the date of first record of appearance of distant metastasis or death for any cause. Local-regional failure or second cancers diagnosed before the distant metastases are not considered events of interest for this endpoint. Subjects alive and free of distant metastasis are censored at the date of the most recent follow-up examination.

8.1.8 *Overall Survival (OS)*

Overall survival is defined as the time from the date of registration to the date of death for any cause. The follow-up of subjects still alive will be censored at the date of last visit/contact.

8.2 *Evaluation of Efficacy*

The efficacy endpoints will be measured clinically and radiologically using the revised international criteria (1.1) proposed by the RECIST (Response Evaluation Criteria in Solid Tumours) committee.

8.2.1 *Measurable Disease*

Categorization of measurable disease will be based on the RECIST 1.1 criteria with clinical examination as appropriate.

Measurable tumour lesions are defined as those that can be accurately measured in at least one dimension (longest diameter to be recorded) as ≥ 20 mm with chest x-ray and as ≥ 10 mm with CT scan or clinical examination. Bone lesions are considered measurable only if assessed by CT scan and have an identifiable soft tissue component that meets these requirements (soft tissue component ≥ 10 mm by CT scan). Malignant lymph nodes must be ≥ 15 mm in the short axis to be considered measurable; only the short axis will be measured and followed. All tumour measurements must be recorded in millimetres (or decimal fractions of centimetres). Previously irradiated lesions are not considered measurable unless progression has been documented in the lesion.

8.2.2 *Non-measurable Disease*

All other lesions (or sites of disease), including small lesions are considered non-measurable disease. Bone lesions without a measurable soft tissue component, leptomeningeal disease, ascites, pleural/pericardial effusions, lymphangitis cutis/pulmonis, inflammatory breast disease, lymphangitic involvement of lung or skin and abdominal masses followed by clinical examination are all non-measurable. Lesions in previously irradiated areas are non-measurable, unless progression has been demonstrated.

8.2.3 *Target Lesions*

When more than one measurable tumour lesion is present at baseline all lesions up to a maximum of 5 lesions total (and a maximum of 2 lesions per organ) representative of all involved organs should be identified as target lesions and will be recorded and measured at baseline. Target lesions should be selected on the basis of their size (lesions with the longest diameter), be representative of all involved organs, but in addition should be those that lend themselves to reproducible repeated measurements. Note that pathological nodes must meet the criterion of a short axis of ≥ 15 mm by CT scan and only the short axis of these nodes will contribute to the baseline sum. All other pathological nodes (those with short axis ≥ 10 mm but < 15 mm) should be considered non-target lesions. Nodes that have a short axis < 10 mm are considered non-pathological and should not be recorded or followed (see 8.2.4). At baseline, the sum of the target lesions (longest diameter of tumour lesions plus short axis of lymph nodes: overall maximum of 5) is to be recorded.

After baseline, a value should be provided on the CRF for all identified target lesions for each assessment, even if very small. If extremely small and faint lesions cannot be accurately measured but are deemed to be present, a default value of 5 mm may be used. If lesions are too small to measure and indeed are believed to be absent, a default value of 0 mm may be used.

8.2.4 *Non-target Lesions*

All non-measurable lesions (or sites of disease) plus any measurable lesions over and above those listed as target lesions are considered non-target lesions. Measurements are not required but these lesions should be noted at baseline and should be followed as "present" or "absent".

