8.4.1 Local Recurrence or Progression

Local failure will be primarily determined by evidence of progression or recurrence clinically or radiologically. For clinical and radiographic assessments, RECIST 1.1 criteria for progressive or recurrent disease shall be used whenever applicable. In the case of nonmeasurable disease or in circumstances where laryngeal edema complicates the interpretation of radiological measurements, unequivocal clinical description of disease progression or recurrence is required. Biopsy proof (fine needle aspirate is not sufficient) of progressive/recurrent disease is desirable but is not essential if progression/recurrence is documented clinically. Any form of surgery at the primary site will be considered local progression/recurrence unless the pathology shows no evidence of disease.

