8.4.2 Regional Lymph Node Recurrence or Progression

Neck dissection performed for clinical or radiological (RECIST 1.1) disease persistence/progression/recurrence within target volumes after 20 weeks from the end of radiation therapy with evidence of tumour present or unknown will be considered a treatment failure.

Neck dissection performed at any time after registration for clinical or radiological (RECIST 1.1) disease recurrence/progression outside the target volumes or without documentation of the site of failure with tumour present/unknown will be considered a treatment failure.

Development of any new clinically or biopsy proven malignant regional nodes not present at baseline or clinically or biopsy proven recurring or progressing nodes will be considered evidence of regional recurrence/progression.

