8.4.3 Out-of-field Regional Failure

An out-of-field regional failure is defined as regional recurrence or progression outside the treatment field. Subjects with clinical or radiological evidence concerning for nodal failure outside the treatment field should have pathologic confirmation and restaging for local and distant disease. A positive biopsy and/or a neck dissection at any time after registration performed for suspected nodal failure outside the treatment field that is positive/unknown for tumour on pathology will be considered out-of-field regional failure. Subjects who do not have a neck dissection because their neck disease is judged to be unresectable will only be deemed to have failure in the neck after biopsy or cytological confirmation is obtained or disease progression is documented.

If failure is not confirmed, subjects may be observed with CT repeated at 3 monthly intervals or following local institutional guidelines to confirm stability or regression of the lymph nodes.

Categorizing regional failure as in-field or out-of-field will be done by the local investigator based on review of the original treatment volumes and the site of tumour recurrence in the neck. Post-hoc central review of the patterns of regional failure will also be performed on all subjects that have regional failure (either as first or subsequent recurrence).

8.4.4 *Local-regional Failure*

This is defined as local failure, regional failure or both. For the purposes of determining site of first failure the category of both will be applicable if local and regional failure occurs within one month of each other.

8.4.5 *Distant Metastasis*

This is defined as the presence of positive pathological or radiological evidence of recurrent disease at any site of the body with the exception of those defined as 'local' or 'regional'.

When distant metastases are the first indication of relapse, then the patient must be examined for local-regional disease.

8.4.6 *Event-Free Survival Endpoint*

First Event	Event-free Survival
None	Censored
Local-regional progression or recurrence	Failure
Distant metastasis	Failure
Non-protocol RT, chemotherapy, or biologic therapy (for the current OPSCC) without documentation of the site of failure	Failure
Surgery of primary site (at any time after RT) with tumour present/unknown	Failure
Neck dissection with tumour present/unknown, > 20 weeks from end of RT	Failure

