13.3 Sample Size and Duration of Study

We estimate 2-year EFS to be 91% (H_a) for low-risk HPV-related OPSCC. Assuming that the experimental treatment will be considered as ineffective if the 2-year EFS is $\leq 85\%$ (H_0), with one-sided alpha of 0.1, a sample size of 100 patients will have 80% power to detect a 6% difference of 2-year EFS. With 3 years of accrual and 2 years of follow-up, the total duration of this study will be 5 years. A total of 304.7 person-years of follow-up is needed for the final analysis. The null hypothesis (H_0) will be rejected when the observed survival rate is 88.85% or higher (i.e. if there are 18 or fewer EFS events observed).

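### Stable residual disease at the primary site that is treated without surgery, with the site recorded, meets no EFS or LRC event, although the same disease counts as a failure if resected.

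*Protocol*

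**What the plan says.** The EFS definition stands in Protocol 8.1.4, is repeated in 8.3.7 and the 8.4.6 table, and is carried into SAP 2.5.1. It has four kinds of event:

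- investigator-determined local-regional progression or recurrence, or distant metastasis;
- certain operations with tumour present or unknown on pathology. Persistence is named only here: surgery at the primary at any time, and in-field neck dissection more than 20 weeks after radiotherapy;
- "Non-protocol RT, chemotherapy, or biologic therapy (for the current cancer diagnosis) without documentation of the site of failure";
- death from any cause.

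LRC (Protocol 8.1.5, SAP 2.5.3) has the surgical events and the first record of local or regional progression or recurrence. It has no non-protocol-therapy event.

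The supporting definitions use the same terms. In 8.4.1, "Local failure will be primarily determined by evidence of progression or recurrence clinically or radiologically". In 8.4.2, besides new malignant nodes and the dissection events, "clinically or biopsy proven recurring or progressing nodes will be considered evidence of regional recurrence/progression". Section 8.3.8 defines progression by growth, new lesions or, exceptionally, unequivocal non-target progression. Section 8.4 states that response is not an endpoint.

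One sentence points the other way. It is in 8.4.3: "Subjects who do not have a neck dissection because their neck disease is judged to be unresectable will only be deemed to have failure". The condition it sets for calling this a neck failure is confirmation by biopsy or cytology, or documented progression.

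**The concern.** The plan itself treats residual cancer as failure when it is resected and found on pathology. If the surgeon judges it inoperable, or the team chooses another treatment, the same residual cancer has no event attached. Status then depends on the treatment chosen, not on the disease. The wording of the therapy event adds an oddity: recording the site of failure removes the patient from the only event that would otherwise apply.

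The situation is foreseeable. Protocol 7.3 makes neck surgery conditional on operability, and 10.2 leaves later therapy to the investigator. Any misclassification favours the treatment, in a single-arm trial whose success rule is a count of 18 or fewer EFS events.

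**Working it through.** **Step 1: trace one patient through the text.** Take biopsy-proven, stable residual tumour at the primary site, no surgery, non-protocol radiotherapy or systemic therapy started, site recorded.

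| Event | Met? | Reason |
|---|---|---|
| Local-regional progression or recurrence (8.1.4, 8.3.8, 8.4.1) | No, as written | No growth, no new lesion, no recurrence after clearance |
| Distant metastasis | No | None present |
| Surgery for persistence | No | No operation |
| Non-protocol therapy | No | Site is documented |
| Death | No | Alive |
| LRC events (8.1.5) | No | Surgical, or progression/recurrence, only |

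If the same tumour is resected with tumour present, the primary-site surgery event is met for both EFS and LRC.

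The list in 8.4.6 of things that are not events does not mention this patient either. In SAP 2.5.1 the hierarchy for simultaneous events, and SAP Table 6, name non-protocol therapy without the site qualifier that the definition carries. An analyst could follow either.

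**Step 2: reproduce the plan's decision rule.** Inputs from Protocol 13.3: null 2-year EFS 85%, alternative 91%, "with one-sided alpha of 0.1", 304.7 person-years, reject the null at 18 or fewer events. Assume exponential EFS and a Poisson event count.

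- Null hazard: -ln(0.85)/2 = 0.08126 per year. Expected events: 0.08126 × 304.7 = 24.76.
- Alternative hazard: -ln(0.91)/2 = 0.04716 per year. Expected events: 0.04716 × 304.7 = 14.37.
- P(X ≤ 18 | mean 24.76) = 0.0999, matching alpha 0.1.
- EFS at the boundary: exp(-2 × 18/304.7) = 88.86%, against 88.85% stated.
- Power: P(X ≤ 18 | mean 14.37) = 0.861 ignoring the interim; P(X ≤ 17) = 0.7999, the stated 80%.

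The model reproduces the rule, so it can be used for sensitivity.

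**Step 3: effect of uncounted failures.** Suppose k true failures are never counted by the cut-off, with person-years held at 304.7. The documents give no rate, so k = 1 to 3 is an assumption. Two ways of removing k events are shown for a true 2-year EFS of 85%.

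| k | Mean reduced: P(X ≤ 18), mean 24.76 - k | Boundary shifted: P(X ≤ 18 + k), mean 24.76 | True 2-year EFS at 18 + k events |
|---|---|---|---|
| 0 | 0.100 | 0.100 | 88.9% |
| 1 | 0.138 | 0.144 | 88.3% |
| 2 | 0.188 | 0.198 | 87.7% |
| 3 | 0.248 | 0.262 | 87.1% |

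The first column is used below; the second is slightly higher. Neither allows for a patient whose event is only delayed.

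**The case against.** The strongest reply is about intent. The phrase on undocumented site looks like a catch-all: where a site is documented, the drafters probably expected the investigator-determined local-regional event to apply. That bullet carries no RECIST condition of its own, 8.4.1 uses RECIST only where applicable, and 11.1 provides central review of endpoints. An investigator who starts salvage for proven cancer may well report local-regional failure. This makes the gap less likely to bite, but the text nowhere says that stable persistence is progression or recurrence.

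Three stronger readings are tempting and are not supported:

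- *Unresectable in-field nodes certainly go uncounted.* The 8.4.3 sentence speaks of neck disease without restricting it to out-of-field disease and accepts biopsy or cytology; 8.4.4 makes regional failure a local-regional failure. But it sits under the out-of-field heading and is not carried into the EFS or LRC lists. The text is ambiguous, not silent.
- *This hides failures of the reduced elective volumes.* Residual primary or gross nodal disease lies in the 70 Gy volumes (7.2.8). The added risk that 7.2.18 names is out-of-field regional recurrence, and that is counted. Persistence reflects the whole regimen, which is still what the primary objective evaluates.
- *The error rate is in fact inflated to 0.14 to 0.25.* The rule counts all events over 304.7 person-years, about three years per patient. Later progression, metastasis or death before the cut-off is still counted. Section 7.3.1 also cites high rates of eventual complete response in the neck.

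**Conclusion.** The gap is real and narrow. For stable residual primary disease treated without surgery at a recorded site, the text gives no EFS or LRC event until progression, metastasis or death. For unresectable in-field neck disease it can be read either way.

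The direction of any bias is towards success; its size is unknown. One, two or three failures never counted by the cut-off would raise the chance of passing at a true 85% from 0.10 to about 0.14, 0.19 or 0.25. These figures assume the number of patients and assume that none has a later counted event, so for each number they are an upper bound. They also rest on the exponential and Poisson model that reproduces the plan's own boundary. With the boundary at 18, one case could decide the result, which justifies settling the wording even if such cases are rare.

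**What to change.** 1. In Protocol 8.1.4, 8.3.7 and 8.4.6 and in SAP 2.5.1, count any non-protocol radiotherapy, chemotherapy or biologic therapy started for persistent, progressive or recurrent study cancer as an EFS event from its start date, whether or not the site is documented, unless an earlier event exists.
2. Add the same event to LRC (Protocol 8.1.5, SAP 2.5.3) when the treated site is local or regional.
3. State that therapy given only as an adjunct to an exempt in-field neck dissection at 20 weeks or earlier is not an event. Otherwise item 1 would undo that exemption.
4. State whether the 8.4.3 sentence on unresectable neck disease applies inside the field.
5. Enrolment is complete (103 patients, SAP 1.6) and the interim analysis has been reviewed (SAP 1.5). So list the affected patients and report the result under both the original and the revised definition.

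**Cost.** The sample size and the 18-event boundary do not change. Relapse reports, pathology and subsequent therapies are already collected (Protocol 10.3, Appendix III). This is still a late change to a primary endpoint definition, hence the dual reporting. The event count may rise slightly. Persistent disease given no further therapy would still not be captured.
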